## 9.10. Other Aspects

Not applicable.

## 10. PROTECTION OF HUMAN SUBJECTS

### 10.1. Patient Information

This study involves data that exist in anonymised structured format and contain no patient personal information.

### 10.2. Patient Consent

As this study involves anonymised structured data, which according to applicable legal requirements do not contain data subject to privacy laws, obtaining informed consent from patients by Pfizer is not required.

### 10.3. Institutional Review Board/Independent Ethics Committee

There must be prospective approval of the study protocol, protocol amendments, and other relevant documents (eg, informed consent forms if applicable) from the relevant Institutional Review Boards (IRB)/International Ethics Committee (IEC). All correspondence with the IRB/IEC must be retained. Copies of IRB/IEC approvals must be forwarded to Pfizer.

This register-linkage database does not contain any patient identification information (eg, name), except for a unique number assigned for the purpose of linking files. This study has been approved by the Ethics Committee in Stockholm (DNR: 2015/1844-31/2, renewed approval will be sought as needed for the duration of the study).

#### 10.3.1. Ethical Permits

In accordance with Swedish law, non-interventional studies of register-based data (including “quality of care” registers such as SRQ/ARTIS) do not usually require informed consent by the individual study subjects. Instead, regional ethics committees are mandated to provide permission for such studies, after weighing the subjects’ potential benefit from the research against the potential risks to the subjects’ personal privacy. ARTIS has ethical approval for the studies described in this protocol as outlined above but is subject to strict rules and regulations regarding the maintenance, analysis and reporting of personal data. Patient consent is not required for this study as data already exist within ARTIS register.

### 10.4. Ethical Conduct of the Study

The study will be conducted in accordance with legal and regulatory requirements, as well as with scientific purpose, value and rigor and follow generally accepted research practices described in Guidelines for Good Pharmacoepidemiology Practices issued by the International Society for Pharmacoepidemiology, Good Epidemiological Practice (GEP) guidelines issued by the International Epidemiological Association, the Karolinska Institutet’s guidelines on Research Conduct and the European Network of Centres for

Pharmacoepidemiology and Pharmacovigilance (ENCePP). See [ANNEX 2. ENCePP checklist for study protocols](#).

## **11. MANAGEMENT AND REPORTING OF ADVERSE EVENTS/ADVERSE REACTIONS**

This study involves data that exist as structured data by the time of study start or a combination of existing structured data and unstructured data, which will be converted to structured form during the implementation of the protocol solely by a computer using automated/algorithmic methods, such as natural language processing.

In these data sources, individual patient data are not retrieved or validated, and it is not possible to link (ie, identify a potential association between) a particular product and medical event for any individual. Thus, the minimum criteria for reporting an adverse event (AE) (ie, identifiable patient, identifiable reporter, a suspect product, and event) cannot be met.

## **12. PLANS FOR DISSEMINATING AND COMMUNICATING STUDY RESULTS**

Annual summary reports will be generated. Analysis using linked register data through 3 years of follow up will be the basis for a final report. Data may be used in regulatory communications external to Sweden for contextualisation purposes. Manuscripts based on specific endpoints of interest may be developed for publication purposes.

In the event of any prohibition or restriction imposed (eg, clinical hold) by an applicable competent authority in any area of the world, or if the investigator is aware of any new information which might influence the evaluation of the benefits and risks of a Pfizer product, Pfizer should be informed immediately.

In addition, the investigator will inform Pfizer immediately of any urgent safety measures taken by the investigator to protect the study patients against any immediate hazard, and of any serious breaches of this NI study protocol that the investigator becomes aware of.

**ANNEX 1. LIST OF STAND ALONE DOCUMENTS**

**Table 3. Endpoint Algorithms and Validation References**

Event	Operationalisation	Validation ICD
Serious infections	Hospitalisations in the Patient Register listing as main diagnosis ICD10-codes below. If main diagnosis is RA, contributory diagnoses are also considered. A00-B99 (excluding A33 and A50), D73.3, E32.1, G00-G02, G04.2, G05-G07, H00.0, H44.0, H60.0-H60.3, H66-H67, H70, I30.1, I40.0, J00-J22, J32, J34.0, J36, J39.0-J39.1, J44.0, J85, J86, K04.4, K04.6, K04.7, K10.2, K11.3, K12.2, K14.0, K57.0, K57.2, K57.4, K57.8, K61, K63.0, K65.0, K65.1, K65.2, K65.9, L00-L08, L30.3, M00-M01, M46.2-M46.5, M60.0, M65.0, M71.0, M71.1, M72.6, M86, N13.6, N15.1, N15.9, N30.0, N30.8, N34.0, N41.2, N43.1, N45.2, N45.3, N45.4, N48.2, N61, N70, N73, N75.1	This algorithm has not been specifically validated in ARTIS, but the register itself is subject to strict quality assurance routines and has been validated several times.  References:  Ludvigsson et al. External Review and Validation of the Swedish National Inpatient Register, BMC Public Health, 2011 (11):450.  http://www.socialstyrelsen.se/register/halsodataregister/patientregistret/inenglish

090177e1953e1418\Approved\Approved On: 16-Oct-2020 13:21 (GMT)

Event	Operationalisation	Validation ICD
CV Risk	Major Acute Cardiovascular Events (MACE), combines MI, stroke, and fatal cardiovascular events: I00-I99 as main cause of death, or I20.0, I21, I60-I64 as diagnosis in in- or outpatient care	
‘Outcome’ was defined as any first-ever ACS event, which in turn was defined as a primary discharge diagnosis of acute myocardial infarction or unstable angina pectoris, or as acute myocardial infarction being the underlying cause of death. For discharge diagnoses, the date of admission to hospital was considered the event date. This outcome definition has previously been validated in a Swedish early RA cohort, with a positive predictive value of 95%. In addition, a regional validation study of hospitalised acute MI and stroke found positive predictive values of 96% and 94% respectively, in the period 1977 to 1987.
 
References:  https://onlinelibrary.wiley.com/doi/epdf/10.1002/art.39267            Mantel et al. Risk Factors for the Rapid Increase in Risk of Acute Coronary Events in Patients With New-Onset Rheumatoid Arthritis. A Nested Case-Control Study. Arthritis & Rheumatology. 2015; 67(11):2845-2854.
 
Lindblad et al. Validity of register data on acute myocardial infarction and acute stroke. Scandinavian Journal of Public health 1993; 21 (1):3-9.

NMSC	
Identified through the Cancer register as all malignancies with ICD-O/2 code C44, and all basal cell cancers recoded in the register’s subcomponent on basal cell cancers
 
Alt: all invasive NMSC, identified as non-benign ICD-O/2 code C44, and no basal cell cancers.
	
About 99% of cancers have been morphologically verified. Reporting of incident cancers (including invasive malignancies as well as cancer in situ) is mandatory and semi-automated, resulting in an estimated coverage greater than 95%.

090177e1953e1418\Approved\Approved On: 16-Oct-2020 13:21 (GMT)

Event	Operationalisation	Validation ICD
Malignancy	All invasive malignancies recorded in the cancer register, excluding NMSC	See NMSC
Abbreviations: ACS= acute coronary syndrome; ARTIS= Anti Rheumatic Treatment in Sweden; ICD= International Classification of Diseases; MACE= major acute cardiovascular events; MI= myocardial infarction; NMSC= non-melanoma skin cancer; RA= rheumatoid arthritis		

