### 9.3.3. Endpoints of Interest

For the interim and final safety reports (which will include information on patients, covariates and incidence rates for pre-specified safety outcomes, from SRQ as well as from the linked Patient/Prescribed Drug and other registers), the following events of interest have been pre-specified.

1. Hospitalised infections overall.
2. NMSC.
3. Malignancies, excluding NMSC.
4. CV events, including but not limited to deep vein thrombosis/pulmonary embolism.
5. Use during pregnancy.

In addition, the final study report will include the number of Ruxience-exposed pregnancies. If data are sufficient, rates of diagnosed malformations can be provided however, the number of Ruxience-exposed pregnancies is expected to be low based on previous data for other biosimilars.

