## 9.7. Data Analysis

All statistical analyses will be performed by ARTIS using SAS version 9.4 or later. Detailed methodology for all analyses of data included in this study will be documented in a Statistical Analysis Plan (SAP), which will be dated, filed and maintained by ARTIS and shared with the Sponsor. The SAP may modify the plans outlined in the protocol; any major modifications of primary endpoint definitions or their analyses would be reflected in a protocol amendment.

ARTIS will apply an ICD-code-based algorithm to identify serious infections, malignancies and CV events (MACE), in the Swedish patient register. See [Table 3. Endpoint Algorithms and Validation References](#) in [ANNEX 1. LIST OF STAND ALONE DOCUMENTS](#) for algorithms and relevant validation references. The specific algorithms for defining those endpoints have not been validated, though the Swedish patient register has been validated several times. The overall positive predictive value (PPV) of the inpatient diagnoses generally ranged from 85% to 95%. A regional validation study of hospitalised acute MI and stroke (components of the MACE endpoint) found PPVs of 96% and 94% respectively, in the period 1977 to 1987. While the ICD algorithms used by ARTIS to define the endpoints of interest may not be validated, their use can be justified given the importance to contextualise the study results with historical findings. ARTIS has previously conducted and published studies of serious infections  and MACE  events in RA patients.

Per Pfizer's subscription to the ARTIS database, analyses will be conducted by ARTIS researchers and in accordance with ARTIS scientific review policies. The database does not contain any patient identification information (eg, name), except for a unique number assigned for the purpose of linking files.

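### Table 3 defines MACE in words as MI, stroke and fatal CV events, but its code list also counts unstable angina (I20.0)

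*Protocol*

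**What the plan says.** The CV Risk row of Annex 1, Table 3 gives the endpoint first in words and then, in the same cell, the codes meant to implement it. MACE "combines MI, stroke, and fatal cardiovascular events: I00-I99 as main cause of death, or I20.0, I21, I60-I64 as diagnosis". The cell goes on to accept those diagnoses from inpatient or outpatient care.

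The validation column of that row describes a different outcome, the acute coronary syndrome (ACS) endpoint of a cited study. Its non-fatal part is "a primary discharge diagnosis of acute myocardial infarction or unstable angina pectoris", and the column gives that outcome a positive predictive value (PPV) of 95% in a Swedish early RA cohort.

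Section 9.7 makes the Table 3 algorithms operative: "ARTIS will apply an ICD-code-based algorithm to identify serious infections, malignancies and CV events (MACE"). It concedes that the specific algorithms have not been validated and says that "their use can be justified given the importance to contextualise the study results with historical findings". No section names unstable angina as a component of this study's MACE.

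**The concern.** The definition and its implementation disagree inside one table cell. An analyst who follows the words counts MI, stroke and CV death. One who follows the codes also counts a living patient with unstable angina and no infarction. The two counts can differ, and both would carry the label MACE.

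This matters because of how the rate will be used. CV disease is an important potential risk in the risk management plan that Section 7 cites. The study has no control group (Section 9.9), so its CV rate has meaning only beside rates from elsewhere. Section 9.7 defends the algorithms on that ground, and Section 12 foresees regulatory use for context. A reader who takes the worded definition at face value and sets the rate beside a three-component MACE rate would be comparing unlike composites.

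**Working it through.** **Step 1: match each code to a named component.** The table does not spell out the codes, so this uses their standard ICD-10 meaning.

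| Code in Table 3 | How it is counted | Named component |
|---|---|---|
| I00-I99 | main cause of death | fatal CV events |
| I21 | inpatient or outpatient diagnosis | MI |
| I60-I64 | inpatient or outpatient diagnosis | stroke |
| I20.0 (unstable angina) | inpatient or outpatient diagnosis | none |

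The fatal component cannot absorb I20.0, because I20.0 enters as a care diagnosis and not as a cause of death. It is not shorthand for MI either: the validation column of the same row lists acute myocardial infarction and unstable angina as alternatives.

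**Step 2: the plan's own CV figure.** Table 2 gives 3 CV events in 73 patients. 3/73 = 0.041, and the exact (Clopper-Pearson) 95% interval is 0.009 to 0.115, as printed. The table does not split the events by type, so it cannot size the mismatch.

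**Step 3: direction.** Section 9.7.2 defines the rate as events divided by person-time. Adding a qualifying code cannot reduce the number of events. If follow-up stops at the first qualifying event, it cannot lengthen person-time. With the same patients at risk under both definitions, the rate as coded is therefore at least the rate as worded.

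**Step 4: size, under an assumption.** Let s be the share of events counted by the code list that qualify only through I20.0. Take person-time as about equal under both definitions.

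Rate as coded / rate as worded = 1/(1 - s), so the relative excess is s/(1 - s).

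- s = 0.05: 0.05/0.95 = 5.3%
- s = 0.10: 0.10/0.90 = 11.1%
- s = 0.20: 0.20/0.80 = 25%

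The values of s are illustrations. The documents give no count of unstable angina.

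**The case against.** The best case for the plan is that I20.0 is deliberate. Section 9.7 wants continuity with earlier ARTIS work, and one of the studies it cites under MACE (reference 30) is, by its title, a study of ACS. The validation column describes an ACS outcome that includes unstable angina. On that view the codes are right and the wording is incomplete, and deleting I20.0 could reduce comparability. This stands as a reason not to insist on deletion. It does not remove the mismatch, because the wording would then need correcting.

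It can also be said that Section 9.3.3 specifies a wider endpoint, "CV events, including but not limited to deep vein thrombosis/pulmonary embolism", which does not exclude unstable angina, and that the codes are printed for anyone to read. Both are true. But Section 9.7 equates the CV events to be identified with MACE, and Table 3 says in words what MACE is. A rate quoted outside the protocol would travel with the label and not with the code list.

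Third, the possible shift is small beside the precision shown. The upper limit in Table 2 is almost 13 times the lower (0.115/0.009 = 12.8), and no test or threshold depends on the rate. This limits the weight of the point. It does not justify leaving two definitions in place, since more data would narrow the interval without resolving them.

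Two stronger readings are tempting, and the documents do not support them:

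- A reader might infer that I20.0 is a less specific component, because the 96% and 94% PPVs are for MI and stroke only. The same row gives 95% for an ACS outcome that includes unstable angina. That figure is pooled and applies to primary discharge diagnoses, so it does not validate I20.0 alone, but nothing in the protocol shows I20.0 to be worse.
- A reader might take Section 9.7 as confirming that unstable angina is excluded: "A regional validation study of hospitalised acute MI and stroke (components of the MACE endpoint"). The phrase does not claim to be complete, and it also leaves out fatal CV events, which are plainly in the composite.

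**Conclusion.** The point holds as an internal contradiction in an operative safety-endpoint definition. As coded, the rate labelled MACE includes events that the worded definition does not, and it can only equal or exceed the three-component rate. The size is unknown: about 5%, 11% or 25% if 5%, 10% or 20% of counted events qualify only through I20.0. This rests on the standard meaning of the ICD-10 codes, on the same patients being at risk under both definitions, and on roughly equal person-time.

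A reader might go on to infer that the extra component would make Ruxience appear to carry an excess CV risk. The documents do not support that. Whether the historical rates include unstable angina depends on sources outside the protocol, and if they do, the composite as coded may be the closer match. Nor do the documents show which of the two, words or codes, is the mistake. The correction is worth making before data extraction, while it costs almost nothing.

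**What to change.** Reconcile the CV Risk row of Table 3 in one of two ways:

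- remove I20.0 from the MACE code list, so that the codes match the three named components; or
- keep I20.0, name unstable angina as a component in the wording, and relabel the composite, for example as ACS, stroke and CV death.

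Whichever is chosen, report the rate with and without I20.0. One version can then be set against three-component MACE and the other against ACS-based historical rates. Make the description of the MACE components in Section 9.7 agree with the choice.

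The cost is one changed table row and one extra result line from the same data extraction. If I20.0 is removed from the headline composite, its event count can fall slightly and its interval widen slightly in relative terms.

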### 9.2.2. Exclusion Criteria

There are no exclusion criteria for this study.

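### The MACE rule in Table 3 accepts inpatient or outpatient codes in any position and does not separate new events from recoded pre-index ones; the PPVs beside it belong to narrower hospital definitions

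*Protocol*

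**What the plan says.** Table 3 in Annex 1 of the Protocol builds MACE from two parts. The fatal part is "I00-I99 as main cause of death". The non-fatal part is "I20.0, I21, I60-I64 as diagnosis in in- or outpatient care". The row describes the composite as MI, stroke and fatal cardiovascular events.

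The serious-infection row of the same table is tighter: "Hospitalisations in the Patient Register listing as main diagnosis ICD10-codes below", with contributory diagnoses considered only when RA is the main diagnosis.

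The validation cell beside MACE describes another outcome: "any first-ever ACS event, which in turn was defined as a primary discharge diagnosis of acute myocardial infarction or unstable angina pectoris", or acute MI as underlying cause of death, with a PPV of 95%. It also cites a regional study, which section 9.7 repeats: "A regional validation study of hospitalised acute MI and stroke (components of the MACE endpoint) found PPVs of 96% and 94% respectively", for 1977 to 1987.

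On prior disease, section 9.2.2 says "There are no exclusion criteria for this study". Section 9.3.2 follows each patient from the Index Date to the outcome and states no look-back or first-ever condition for CV events. Section 9.4.3 says that the Patient Register holds all non-primary outpatient visits. Section 9.7.2 defines the result as events divided by person-time of exposure.

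**The concern.** Read as written, a patient whose MI or stroke preceded treatment becomes a MACE case if a listed code is entered at any specialist visit inside the risk window. That would be prevalent disease counted as incident. Section 9.9 expects that patients with comorbidities may be channelled to the drug, so the patients most exposed to this error may be over-represented.

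The study has no control group, so a definitional error cannot cancel in a comparison; the absolute rate is the product. Section 12 allows the data to be used in regulatory communications. A reader who sees PPVs of 94-96% next to the MACE row may take them as the accuracy of that row.

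**Working it through.** **1. The MACE rule against the evidence cited for it**

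| Feature | MACE rule (Table 3) | ACS validation, PPV 95% | MI/stroke validation, PPV 96%/94% |
|---|---|---|---|
| Setting | inpatient or outpatient | hospital discharge | hospitalised |
| Diagnosis position | none stated | primary | none stated |
| First-ever | not required | required | not stated |
| Non-fatal events | I20.0, I21, I60-I64 | acute MI, unstable angina | acute MI, stroke |
| Deaths | any I00-I99 as main cause | acute MI as underlying cause | not stated |
| Period | current, ICD-10 | not stated in the Protocol | 1977-1987, before ICD-10 (in use since 1997, section 9.4.3) |

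Neither definition matches the rule. The general 85-95% PPV in section 9.7 is also for inpatient diagnoses, and no PPV is given for outpatient codes. That any diagnosis position counts is the literal reading of an unrestricted rule, supported by the contrast with the infection row; the words themselves are not printed.

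**2. Can a pre-index event be counted?** No exclusion criterion, look-back or first-ever rule removes it, and follow-up ends at the first qualifying outcome. A recoded old event therefore counts, at most once per patient.

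**3. The only CV frequency in the Protocol.** Table 2 (section 9.5) gives 3 events in 73 patients. 3/73 = 0.041, and the exact (Clopper-Pearson) 95% interval is 0.009 to 0.115, as printed. Table 2 calls these CV events and does not say that they are MACE. Section 9.3.3 describes CV events as including, without being limited to, venous thromboembolism. The figure serves only as a scale.

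**4. Illustration of size.** Let t = 3/73 be the true proportion, h the share with a prior MI or stroke, and q the chance that the old event is recoded inside the risk window. Neither h nor q is in the Protocol; the ranges h = 3-15% and q = 5-50% are assumptions.

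Observed = t + h × q × (1 − t); inflation = observed / t; PPV = t / observed.

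| h | q | Observed | Inflation | PPV |
|---|---|---|---|---|
| 3% | 5% | 0.0411 + 0.0015 × 0.9589 = 0.0425 | 1.04 | 97% |
| 10% | 10% | 0.0411 + 0.0100 × 0.9589 = 0.0507 | 1.23 | 81% |
| 15% | 50% | 0.0411 + 0.0750 × 0.9589 = 0.1130 | 2.75 | 36% |

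Solving for the recoding that yields a given PPV, h × q = t × (1/PPV − 1) / (1 − t). For 95% this is 0.0411 × 0.0526 / 0.9589 = 0.0023, and for 80% it is 0.0411 × 0.25 / 0.9589 = 0.0107. On this scale, false events in about 1.1% of the cohort would bring the PPV down to 80%. One false event in 73 patients would move 0.041 (0.009 to 0.115) to 4/73 = 0.055 (0.015 to 0.134).

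**The case against.** The Protocol is open about validity. Section 9.7 says that the specific algorithms have not been validated, dates the MI and stroke study, and labels the general PPV as inpatient. Section 9.9 names endpoint misclassification as a particular concern. Section 9.7 also gives a reason for the algorithms: results need to be set against historical findings. A reader might infer that the Protocol passes its MACE rule off as validated. It does not, and that reading should be dropped. What remains is that the table does not say which definition each PPV belongs to.

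Nothing in the Protocol shows that old events are in fact recoded with these codes at follow-up visits. This stands: old events can enter the numerator, but it is not established that they do.

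Keeping patients with a prior MI or stroke in the cohort is legitimate, since a recurrent event on treatment is a genuine safety event. This also stands. The absence of exclusion criteria is not itself the fault; the missing separation of new from old events is.

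Look-back and diagnosis-position rules could be left to the SAP, which is not at hand. This carries less weight, because Table 3 already states the algorithm, and section 9.7 says that major changes to primary endpoint definitions would be reflected in a protocol amendment. The ENCePP checklist in Annex 2 also marks control of outcome misclassification (10.6) and sensitivity analyses (10.8) as not applicable.

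**Conclusion.** The point holds as a definitional weakness that is cheap to repair. Followed as written, Table 3 can count a pre-index MI or stroke as an incident MACE, and the supporting PPVs describe narrower hospital-based outcomes. The direction of the bias is upward. Its size is unknown: the 1.04- to 2.75-fold range rests on assumed prior-event prevalence and recoding, and on a base proportion not stated to be MACE.

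Two stronger conclusions are tempting. One is that the reported rate will be inflated several-fold; the documents contain no prevalence or recoding figure that would support it. The other is that a validated replacement is available in the table. It is not: the 95% PPV covers first-ever ACS, including unstable angina, with MI deaths only and no stroke, and the 96% and 94% figures carry no stated diagnosis position. A hospital-based MACE composite would lie closer to that evidence but would still be unvalidated.

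**What to change.** In Table 3:

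- Report MACE with non-fatal events defined as a hospitalisation with a listed code as main diagnosis, dated at admission, plus cardiovascular death, counting the first event after the Index Date.
- Present that rate also by presence or absence of a listed diagnosis in the Patient Register before the Index Date.
- Keep the current inpatient-or-outpatient version alongside, for comparability with earlier ARTIS reports.
- State which definition each PPV belongs to, and do not call the new composite validated.
- If I20.0 is kept, name unstable angina in the label.

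The cost is a change of wording in Table 3 and one extra programme run, because the Patient Register linkage is already planned and comorbidity history is already baseline data (section 9.3.1). The downside is that some true events coded only in outpatient care or in a secondary position will appear only in the broader version.
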